2.3 Sample size

The primary clinical outcome will be analysed using rank-based methods, with death at 30 days ranked as the worst outcome. To achieve 90% power, using simulations based on data from the Oxy-PICU pilot RCT, to detect a clinically meaningful reduction in the mean duration of organ support of 12 hours from 120 to 108 hours and assuming no impact on 7.5% mortality requires a total sample size of 2040 patients (allowing for withdrawal/refusal of deferred consent of 10%).

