3.1 Confidence intervals and p-values

The primary clinical outcome will be tested for superiority. Other secondary outcomes will be tested for superiority, where testing is specified, or summarised and reported using descriptive statistics. Statistical tests will be two-sided with significance set at P<0.05 unless otherwise specified. Effect estimates will be reported with 95% confidence intervals. There will be no adjustment for multiple testing. The results of subgroup analyses will be interpreted taking into account accepted criteria for credible subgroup effects²,³.

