5.2 Clinical effectiveness analysis methods

5.2.1 Primary outcome

The primary clinical outcome will be compared between arms using a Wilcoxon rank-sum test with two-sided p-value of 0.05. The primary effect estimate will be the probabilistic index (the probability that the intervention is superior to the control for either mortality and/or duration of organ support), which will be presented with a 95% confidence interval.

Ordered logistic regression will be used firstly in a sensitivity analysis to estimate the unadjusted proportional odds ratio, and secondly to estimate the proportional odds after adjusting for the following baseline variables:

- age (<12 months / ≥12 months);
- primary reason for admission (lower respiratory tract infection vs. Other);
- severity of abnormality of gas exchange: SF ratio <221 with PEEP ≥5 vs. Other
- predicted mortality at PICU admission (measured using the PIMS 3⁴ score)
- site (as a random effect)

Subgroup analyses will be performed to test for interactions between the effect of allocated treatment group and the following baseline covariates:

- age (<12 months / ≥12 months);
- Age adjusted heart rate centile
- Haemoglobin level at admission

The interaction effect for continuous covariates (haemoglobin at admission) will be illustrated by calculating the adjusted hazard ratio within five categories at quintiles of the continuous variable. Heart rate will be corrected for age by grouping into centile bands⁵.

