Patients who withdrew or withheld consent from data collection will not be included in the primary clinical endpoint analysis, but will be included in sensitivity analyses, firstly with all patients in the intervention group with missing outcomes assumed to have died by day 30, and all patients in the control group assumed to have survived with no further days of organ support, and secondly with the opposite assumptions, to give the absolute range of how much the results could change if the data were complete.

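### SAP 5.4 restores children without data consent only through two opposite extremes, which cannot separate a robust primary result from a fragile one if exclusions near 10%

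*SAP*

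**What the plan says.** SAP 3.3 excludes from the primary analysis children for whom access to records was refused or could not be obtained. SAP 5.4 returns them in sensitivity analyses only. In the first, the text reads "firstly with all patients in the intervention group with missing outcomes assumed to have died by day 30", and the missing control children are taken as alive and free of support from then on. The second swaps the arms. The stated purpose is "to give the absolute range of how much the results could change if the data were complete".

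The sample size in SAP 2.3 includes an allowance, "allowing for withdrawal/refusal of deferred consent of 10" per cent. Under SAP 5.1.1 a death scores 31 and a survivor scores days of support up to 30. SAP 4.4 and 4.5 keep data recorded before refusal or withdrawal, and SAP 4.4 puts the consent approach usually within 24-48 h of randomisation. The primary test in SAP 5.2.1 is a "Wilcoxon rank-sum test with two-sided p-value of 0.05", with the probabilistic index as the effect estimate.

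No other final analysis covers these children. The missing-day scenarios in SAP 5.4 are for the interim, the location rule fills missing support days, the multiple imputation for the clinical analysis covers baseline variables only, SAP 5.2.3 changes the duration definition, and the per-protocol set in SAP 3.3 concerns eligibility and treatment decisions.

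**The concern.** The trial is open and consent follows randomisation, so refusal may depend both on allocation and on how the child is doing. This is the main departure from intention to treat, and readers will want to know whether the result survives a plausible difference between the excluded children in the two arms. The plan offers nothing between leaving them out and assuming 100% mortality in one arm's excluded children against 0% in the other's. If both bounds are expected to be significant, in opposite directions, with and without a real effect of the planned size, that question goes unanswered. A sound positive result would then be published beside an analysis showing significant harm.

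**Working it through.** **Inputs from the SAP.** Section 2.3: "To achieve 90% power, using simulations based on data from the Oxy-PICU pilot RCT"; "reduction in the mean duration of organ support of 12 hours from 120 to 108 hours"; "assuming no impact on 7.5% mortality requires a total sample size of 2040 patients". Section 2.2: 1:1 allocation, so 1020 per arm. At 10% excluded, 102 per arm are missing and 918 are observed.

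**The plan's own figure.** 1836 / 0.90 = 2040, so the inflation is right. The 1836 rests on pilot data that are not shown and cannot be reproduced independently. A log-normal duration with CV 0.6, converted to calendar days with 7.5% deaths at 31, gives 91% Wilcoxon power at 918 per arm, but that CV was chosen to fit.

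**Assumptions.** Duration is log-normal with CV 0.6, 0.7 or 1.0 (also gamma with CV 0.66). Excluded children taken as alive keep 1-3 support days (range checked: day 1 only, up to 5 days).

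**Implied mortality at 10% missing.** 0.9 × 7.5% + 10% = 16.75% in one arm against 0.9 × 7.5% = 6.75% in the other. The design assumes 7.5% in both.

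**Index in the adverse scenario.** With missing fraction m and observed index PI,

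PI(adverse) = (1−m)² × PI + m(1−m) × (0.075/2 + q).

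The 0.075/2 is the half credit when an assigned death ties with an observed control death. The term q is the chance that an observed intervention child scores better than an excluded control child credited with 1-3 days, with ties counted half. Missing against missing contributes 0. At CV 0.6, q is about 0.037 under no effect and 0.050 at the design effect.

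- No effect: 0.81 × 0.500 + 0.09 × (0.0375 + 0.037) = 0.412.
- Design effect: 0.81 × 0.544 + 0.09 × (0.0375 + 0.050) = 0.449.

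The standard error of the index without ties is √(2041 / (12 × 1020²)) = 0.0128. The tie correction lowers it slightly, which gives the z values below.

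**Expected results, 10% missing, days 1-3 kept** (index, z in brackets):

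| True effect | CV | Primary | Adverse | Favourable |
|---|---|---|---|---|
| None | 0.6 | 0.500 (0) | 0.412 (−6.96) | 0.588 (+6.96) |
| None | 1.0 | 0.500 (0) | 0.418 (−6.47) | 0.582 (+6.47) |
| 12 h benefit | 0.6 | 0.544 (3.32) | 0.449 (−4.04) | 0.624 (+9.79) |
| 12 h benefit | 0.7 | 0.539 (2.92) | 0.446 (−4.24) | 0.618 (+9.33) |
| 12 h benefit | 1.0 | 0.530 (2.22) | 0.443 (−4.45) | 0.606 (+8.37) |
| 24 h benefit | 0.6 | 0.593 (6.94) | 0.489 (−0.83) | 0.663 (+12.88) |
| 24 h benefit | 1.0 | 0.562 (4.66) | 0.472 (−2.21) | 0.633 (+10.46) |
| 36 h benefit | 0.6 | 0.645 (10.84) | 0.534 (+2.67) | 0.705 (+16.21) |
| 36 h benefit | 1.0 | 0.598 (7.37) | 0.504 (+0.30) | 0.662 (+12.78) |

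In the three 12 h rows the adverse scenario shows significant harm in 98-99% of trials.

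**Lower exclusion rates, 12 h benefit** (log-normal CV 0.7 and gamma CV 0.66). The adverse z is about +2.3 and +2.1 at 1%, +1.6 and +1.3 at 2%, about 0 at 4%, −0.7 and −0.8 at 5%, and −2.1 and −2.2 at 7%. At 5%, significant harm appears in 10-13% of trials, while the chance that benefit stays significant is about Φ(−0.7 − 1.96), below 1%.

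**A plausible difference, for contrast** (CV 0.6, 12 h benefit, 10% excluded). Give excluded intervention children twice the mortality (15% against 7.5%) and otherwise their own arm's distribution. This turns 0.1 × 0.075 = 0.0075 of the arm from survivors into deaths. A survivor's average index is (0.544 − 0.075 × 0.0375) / 0.925 = 0.585, so the index falls by 0.0075 × (0.585 − 0.0375) = 0.0041, or about 0.33 in z. Restoring all 1020 per arm first lifts z from 3.32 to 3.32 × √(1020/918) = 3.50, leaving about 3.17. Simulation agrees: the share of trials showing benefit goes from about 90% in the primary analysis to 88%. The planned adverse bound for the same trial has z −4.04.

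**The case against.** The strongest reply is that the SAP offers the pair as an absolute range, and that best-case and worst-case bounds do exactly that. No section makes significance in both scenarios a criterion of robustness. A test at 5% follows only from the general rule in SAP 3.1 ("Statistical tests will be two-sided with significance set at P<0.05 unless otherwise specified"), and the bounds can be reported as an index with its interval. Around a null result, opposite extremes ought to straddle 0.5. All of this stands; the bounds are not wrong.

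A reader might go further and infer any of the following, none of which the documents support.

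- *The bounds reverse the result whatever the treatment does.* They do not. At 10% missing and CV 0.6, the adverse bound is not significant for a 24 h benefit and is significant for benefit at 36 h. A 36 h harm brings the favourable bound to z −0.04.
- *Outcomes are assigned purely by arm.* Support days recorded before refusal are kept (SAP 4.4, 4.5). If 5 days are already recorded, the adverse z at the design effect and 10% missing is only −1.0 to −1.6.
- *10% of children will be excluded.* The allowance covers withdrawal and refusal of any kind. Children refused only for trial continuation can stay in the analysis (SAP 4.4), so exclusions may be fewer.
- *The bounds can never test the result.* At about 1-2% missing they carry information at the design effect.

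What survives the reply is narrower: the bounds are the only analysis planned for these children, and near the rate the SAP itself allows for they do not discriminate.

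**Conclusion.** The point holds in a limited form. If exclusions approach 10% with refusal at about days 1-3, the two scenarios are expected to be significant in opposite directions under no effect (|z| about 6.5-7.0) and under the 12 h design effect (adverse z about −4.0 to −4.5). At about 5% the adverse scenario almost never preserves a design-size benefit, though it usually stops short of significant harm. The bounds regain value at about 1-2% missing, for effects of roughly twice the design size or more at intermediate rates, or when more support days precede refusal.

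The sizes rest on an assumed duration shape, because the pilot data are not shown, and on the assumed timing of refusal. The direction is the same across all four shapes tried. This is a gap worth closing before unblinding, not an error in the primary analysis.

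**What to change.** In SAP 5.4, keep the two extreme scenarios as descriptive bounds on the probabilistic index and state that they are not tests of robustness. Add a pre-specified tipping-point analysis for the excluded children:

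- impute their composite score from the observed distribution in their own arm, keeping deaths and support days recorded before refusal;
- vary 30-day mortality and support days among them, separately by arm, over a stated grid (for example mortality from 0 to 4 times the observed rate and a shift of −5 to +5 days; the trial team should choose its own limits);
- report the probabilistic index with 95% CI over the grid, and the smallest between-arm difference among excluded children that would change the conclusion.

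The cost is a few sentences, a short loop over imputed data sets, one more table or plot, and the need to fix the grid in advance. It needs no new data and no extra patients.

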3.3 Analysis Population

Following the intention to treat (ITT) principle, all randomised patients will be included in the analysis of the primary clinical endpoint, excluding only those where consent to access medical records was withheld or unobtainable (or were lost to follow-up before PICU discharge for any other reasons) before 30 days post randomisation.

A sensitivity analysis will be conducted in the per-protocol (PP) population, consisting of all randomised patients excluding those who were found to have breached the eligibility criteria following randomisation, and those where a clinical decision not to follow the trial treatment was recorded immediately post randomisation.

4 Trial population

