5.4 Handling of missing data

The amount of missing data for the survival component of the primary clinical outcome is assumed to be minimal. Patients who consent to data collection and were subsequently lost to follow-up after discharge from PICU but before 30 days are assumed to be alive at day 30 with no subsequent PICU readmissions. All patients discharged from hospital before day 30 are assumed to have survived to day 30.

Where a single day of organ support data is missing, but the patient has known to have received organ support on the previous and next day, we will assume that organ support was also received on the missing day. We will also assume that no organ support was given on the day of hospital discharge, unless otherwise recorded.

For the interim analysis, a complete case analysis will be presented (including only patients with complete data for the primary clinical endpoint, after making the above assumptions), and additional sensitivity analyses will be performed showing results under three different possible scenarios: i) on days where organ support data is missing, at least one form of support was provided if the child was known to be in a PICU, and not given otherwise (regardless of treatment allocation), ii) organ support is provided on all missing days for patients in the conservative arm and not provided for all missing days for patients in the liberal arm, and iii) organ support is not provided on all missing the conservative arm and is provided for all missing days for patients in the liberal arm.

For the final primary clinical analysis where organ support data is missing, we will assume that organ support was given if the patient was known to be located in a PICU/HDU or the location was not known, and organ support was not given if the patient was known to be located on a ward (or was

discharged from PICU/HDU to a ward). The validity of these assumptions will be explored by describing patterns of known organ support by location of care.

For the adjusted analysis, missing baseline variables will be imputed using the Multivariate Imputation using Chained Equations (MICE) algorithm, with the model including all baseline variables included in the adjusted models. The number of imputations will be determined according to level of missingness. Models will be fitted in each imputed dataset and results combined using Rubin's rules.

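### The best/worst-case range in SAP section 5.4 is called absolute, but it restores only some of the children excluded under section 3.3, so it does not bound the complete-data result

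*SAP*

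**What the plan says.** **Who is left out of the primary analysis.** Section 3.3 describes an intention-to-treat analysis "excluding only those where consent to access medical records was withheld or unobtainable", and adds in parentheses those who "or were lost to follow-up before PICU discharge for any other reasons) before 30 days post randomisation". That is three routes out: consent withheld, consent unobtainable, and loss while still in PICU for some other reason.

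**Who is put back.** The last paragraph of section 5.4 reads in part: "Patients who withdrew or withheld consent from data collection will not be included in the primary clinical endpoint analysis, but will be included in sensitivity". Two scenarios follow. The first has "all patients in the intervention group with missing outcomes assumed to have died by day 30", while the corresponding control children are taken to have lived and to have needed nothing more. The second reverses the arms. The stated aim is "to give the absolute range of how much the results could change if the data were complete".

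**What is fixed without variation.** Children lost after PICU discharge but before day 30 "are assumed to be alive at day 30 with no subsequent PICU readmissions". Section 5.4 also treats every child discharged from hospital before day 30 as a survivor. For the final analysis it fills missing organ-support days from the known or unknown location of care.

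**The concern.** The list of exclusions and the list of restorations do not match. Two excluded groups have no extreme value assigned to them, and neither is obviously harmless. Consent is sought after randomisation, at a time that section 4.4 says depends on the child's clinical situation, so failure to obtain it could be related to outcome. A child lost before PICU discharge was still in intensive care when last seen. Death scores 31, the worst rank (section 5.1.1), so a modest number of unseen deaths can move a rank-based estimate.

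A range called absolute will be read as the furthest the result could lie with nobody missing. If some randomised children are outside the calculation, the true limits are wider than those reported.

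**Working it through.** **Step 1. Set the exclusions against the rules that might cover them.**

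| Group | In primary analysis? | In the section 5.4 extremes? |
|---|---|---|
| Consent withheld or withdrawn | No | Yes |
| Consent unobtainable | No (section 3.3) | Not named |
| Lost before PICU discharge, other reason | No (section 3.3) | Not named |
| Lost after PICU discharge, before day 30 | Yes, fixed as alive | Not varied |
| Missing support days, final analysis | Yes, filled by location | Not varied |

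No other rule closes the gap. The alive-at-day-30 rule starts only at PICU discharge. The location rule fills support days, not deaths, and operates in an analysis from which section 3.3 has already removed these children. The arm-specific scenarios given for the interim analysis vary support days only, and only at the interim look.

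**Step 2. The plan's own figure.** Section 2.3 gives 2040 patients including a 10% allowance for withdrawal or refusal of deferred consent. 2040 × 0.90 = 1836 analysable, or 918 per arm, and 1836 / 0.90 = 2040, so the allowance is consistent. The 1836 itself came from simulation on pilot data not shown and cannot be checked. No stated number is disputed.

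**Step 3. Standard error.** For the probabilistic index (PI) with 918 per arm, ignoring ties: SE = √[(1/12)(2/918)] = 0.0135.

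**Step 4. Effect of adding children at the extremes.** Let f be the fraction of each arm placed at the extremes, PI₀ the observed index, d = 0.075 the mortality (section 2.3), and p the share of observed children at the best score (assumed 0.05; not in the SAP). With intervention children set to death and control children to the best score:

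- lower limit = (1−f)²·PI₀ + f(1−f)(d/2 + p/2)
- upper limit = (1−f)²·PI₀ + f(1−f)(2 − d/2 − p/2) + f²

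For f = 0.01 and PI₀ = 0.50: lower = 0.9801 × 0.50 + 0.0099 × 0.0625 = 0.4907, a shift of 0.0093 or about 0.7 SE.

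A simulation using the design values (108 against 120 hours, 7.5% mortality, gamma durations with shape 0.7 to 4, favourable extreme set at a score of 2) gives PI₀ of about 0.52 to 0.55 and a shift of about 0.007 to 0.010 per 1% per arm. Dividing by 0.0135 gives 0.5 to 0.75 SE.

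**Step 5. How far short the range could fall.** Suppose 204 children are excluded in all, added to 1836 observed, with PI₀ = 0.50. Restoring all 204 (f = 0.10): lower = 0.81 × 0.50 + 0.09 × 0.0625 = 0.411, and by symmetry upper = 0.589. The split of the 204 below is purely illustrative.

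| Left out of the extremes | Range as written | Shortfall at each limit |
|---|---|---|
| 0 | 0.411 to 0.589 | none |
| 10 | 0.414 to 0.586 | 0.3 SE |
| 20 | 0.418 to 0.582 | 0.6 SE |
| 51 | 0.431 to 0.570 | 1.5 SE |
| 102 | 0.452 to 0.548 | 3.1 SE |

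Taking p as 0 or 0.10 moves the limits by about 0.002. The favourable extreme is no further support, not no support, so children already supported for several days would move the limits less than this.

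**The case against.** **A wider reading of section 5.4.** Withheld could be shorthand for any consent not given, the scenarios speak of patients with missing outcomes, and the stated aim is complete data. The intent may well have been to cover everyone. That does not rescue the text: section 3.3 lists withheld and unobtainable as alternatives, and loss for other reasons is not a consent decision on any reading. If the wider meaning is intended, a few words would secure it.

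**The affected groups may be tiny.** This stands as a limit on size. Section 5.4 expects little missing survival data, and the 10% in section 2.3 is for withdrawal or refusal, which is the group already restored. It does not measure the gap. The SAP does not define unobtainable, so a link with death is plausible but not shown.

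**Stronger readings that a reader might infer, and that the SAP does not support:**

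- *That these children appear in no analysis at all.* Sections 3.3 and 5.6 define a per-protocol population, also used for safety, that does not name them as excluded, though it gives no rule for their missing outcome. The 90-day and 12-month mortality analyses in section 5.2.2 censor at last follow-up, so children lost in PICU can contribute.
- *That the extremes always cross the null and so tell us nothing.* At f = 0.10 the lower limit is 0.81·PI₀ + 0.0056, which stays above 0.5 once PI₀ exceeds (0.5 − 0.0056)/0.81 = 0.61. Crossing is expected near the design effect at 10% loss, but not for every effect or every loss.
- *That the primary result is biased or its robustness falsely stated.* The SAP makes no robustness claim, and no bias is demonstrated.

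**Conclusion.** The point holds as a mismatch between sections 3.3 and 5.4. The range is not a bound if even one child is excluded for unobtainable consent or loss in PICU, or if any assumed-alive child or location-filled support day could in truth be otherwise. The primary test and estimate are unaffected; what would be misdescribed is a sensitivity analysis.

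The size cannot be fixed from the SAP. The per-1% figure rests on the assumed duration distributions, the 7.5% mortality and full use of both extremes. At a handful of children the shortfall is small; at several per cent it would be more than one standard error. This should be corrected before the outcome data are inspected.

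**What to change.** In the last paragraph of section 5.4, replace the opening description of the patients with wording such as: *All randomised patients not included in the primary clinical endpoint analysis for any reason given in section 3.3 (consent withheld, withdrawn or unobtainable, or lost to follow-up before PICU discharge)*. Apply both scenarios to all of them.

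In the same two scenarios, vary the children lost after PICU discharge who are otherwise fixed as alive. Either vary the location-based support days too, or state that the range is conditional on that rule.

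If these changes are not wanted, delete the claim of an absolute range and say which exclusions the scenarios cover. Reporting the number excluded by reason and arm beside the range would let readers judge how much it matters.

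The cost is SAP wording, a few extra runs and a wider reported range, with no new data. A tipping-point analysis, stepping the assumed death rate separately by arm, would be a useful option but is not needed to correct the error.
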